APPENDIX B: Investigator Reports Required Under an IDE

Under an IDE, the Investigator is required under 21 CFR 812.150 and 21 CFR 812.140 to make the following Reports:

Reports	Submitted To	Comments
Unanticipated Adverse Device Effects	
Reviewing IRBSponsor	Within 10 working days of learning of the adverse effect
Withdrawal of IRB Approval	
Sponsor	Within 5 working days of notification
Deviations from the Investigational Plan in an Emergency	
SponsorReviewing IRB	Within 5 working days of occurrence
Informed Consent (Use of a Device prior to obtaining Informed Consent)	
SponsorReviewing IRB	Within 5 working days after use occurs
Progress Report	
Sponsor, MonitorReviewing IRB	Regularly and at least yearly
Final Report	
SponsorReviewing IRB	Within 3 months after termination or completion of Study
Records Maintenance Transfer	
FDA	Within 10 working days after transfer occurs
Others as requested by IRB or FDA	
FDAReviewing IRB	

Study Reference Number E7080

Statistical Analysis Plan for Protocol E7080: Post-FDA Approval Clinical Trial Evaluating Bronchial Thermoplasty in Severe Persistent Asthma

NCT: NCT01350336

Document Date: 27 Jun 2016

THESE DOCUMENTS ARE THE PROPERTY OF BOSTON SCIENTIFIC CORP. AND SHALL NOT BE REPRODUCED, DISTRIBUTED, DISCLOSED OR USED FOR MANUFACTURE OR SALE OF APPARATUS WITHOUT THE EXPRESS WRITTEN CONSENT OF BOSTON SCIENTIFIC CORP.

Boston Scientific
PAS2 Study Statistical Analysis Plan
90994075 Rev/Ver AB
Page 1 of 15

Statistical Analysis Plan

Post-FDA Approval Clinical Trial Evaluating Bronchial Thermoplasty in Severe Persistent
Asthma
PAS2

Study Reference Number E7080 (BSC), 10-02 (Asthmatx)

CONFIDENTIAL

DO NOT COPY OR DISTRIBUTE WITHOUT WRITTEN PERMISSION

TABLE OF CONTENTS

PROTOCOL SUMMARY	4
1 INTRODUCTION	6
2 ENDPOINT ANALYSIS.....	6
2.1 Primary Endpoint	6
2.1.1 Hypotheses	6
2.1.2 Sample Size.....	6
2.1.3 Statistical Methods.....	7
2.2 Secondary Endpoints.....	8
2.2.1 Hypotheses	9
2.2.2 Statistical Methods.....	9
3 GENERAL STATISTICAL METHODS	9
3.1 Analysis Sets	9
3.2 Control of Systematic Error/Bias	9
3.3 Number of Subjects per Investigative Site.....	9
4 ADDITIONAL DATA ANALYSES.....	9
4.1 Interim Analyses	9
4.2 Subgroup Analyses.....	10
4.3 Justification of Pooling.....	10
4.4 Multivariable Analyses	10
4.5 Other Analyses	10
4.6 Safety Analyses.....	11
4.7 Changes to Planned Analyses	12
5 Validation.....	12
6 Programming Considerations.....	13
6.1 Statistical Software.....	13
6.2 Format of Output.....	13
6.3 Methods for Handling Missing Data.....	13
6.4 Identification of Severe Exacerbations (SE)	13
6.5 Medication Dose Conversions	14
7 Revision History	15

PROTOCOL SUMMARY

Objective(s)	The objective of this study is to evaluate durability of treatment effect and to continue to evaluate the short-term and longer-term safety profile of the Alair System in the United States and Canada in the intended use population (patients 18 years and older with severe persistent asthma) following FDA approval.
Test Device	Alair System for Bronchial Thermoplasty
Control Device	None
Study Design	This will be an open-label, single arm study designed to demonstrate durability of the treatment effect and to evaluate the short-term and longer-term safety profile of the Alair System in the United States and Canada in the intended use population (patients 18 years and older with severe persistent asthma).
Planned Subjects/ Centers/ Countries	Up to 300 subjects (minimum of 250 subjects) will be enrolled to achieve at least 200 evaluable study subjects, accounting for a 20% drop-out rate over 5 years. The study will be conducted at a minimum of 15, and a maximum of 30, centers in the United States and Canada, limiting the number of subjects enrolled in Canada to no greater than 20%.
Primary Endpoints	The primary endpoint will be the proportion of subjects experiencing severe exacerbations during the subsequent 12 month (for Years 2, 3, 4, and 5) compared to the first 12 month after the Alair treatment.
Patient Success Criteria	The primary statistical objective is to demonstrate that the proportion of subjects who experience severe exacerbations in the subsequent 12-month follow-up (for Year 2, Year 3, Year 4 and Year 5 [in 12-month periods]) is not statistically worse when compared with the proportion of the first 12-months, which begins 6-weeks after the last Alair treatment. This objective will be met if the upper 95% confidence limit of the difference in proportions (i.e., the subsequent 12-month proportion minus the first 12-month proportion) is less than 20%.
Secondary Endpoints	The secondary endpoints will include the following additional safety endpoints which will be evaluated annually through Year 5 following treatment with the Alair System: 
 • Rates of Severe exacerbations (exacerbations / subject / year) • Respiratory adverse events* (rates of respiratory adverse events, and proportion of subjects with respiratory adverse events)

Study Reference Number E7080

	
• Emergency room visits for respiratory symptoms (rates of emergency room visits and proportion of subjects with emergency room visits for respiratory symptoms)• Hospitalizations for respiratory symptoms (hospitalizations/ subject/ year and the proportion of subjects with hospitalizations for respiratory symptoms)• Respiratory Serious Adverse Events (detailed narratives will be provided for each event)• Pre- and post-bronchodilator FEV₁ 
* A respiratory adverse event is defined as any sign, symptom, illness, clinically significant abnormal laboratory value, or other adverse medical event associated with the “Respiratory System” that appears or worsens in a subject during a clinical study, regardless of whether or not it is considered related to the procedure used as part of the protocol.

Follow-up Schedule	A follow-up evaluation will be conducted at 6 weeks after the last treatment session. At this time, the 5 year follow-up phase will begin. Subjects will be contacted via phone every 3 months to solicit for adverse events and asthma status. An in-office follow-up evaluation will be performed annually starting after the 6 week evaluation.
Study Duration	Subjects treated with the Alair System will be followed for 5 years after the final procedure.

1 INTRODUCTION

This statistical plan addresses the planned analyses for the PAS2 Trial based on the protocol # 90889079. Specified analyses may be used for scientific presentations and/or manuscripts and may not all be provided to Regulatory Authorities.

2 ENDPOINT ANALYSIS

2.1 Primary Endpoint

The primary endpoint will be the proportion of subjects experiencing severe exacerbations during the subsequent 12-month period (for Years 2, 3, 4, and 5) compared to the first 12-month period after the Alair treatment.

Note: Severe exacerbation is defined as worsening of asthma symptoms requiring use of systemic corticosteroids (tablets, suspension, or injection). For subjects already taking oral corticosteroids on a daily or alternate day basis, a severe exacerbation will be defined as a worsening of asthma symptoms requiring any increase in daily dose of systemic corticosteroids. For consistency, courses of corticosteroids separated by 1 week or more will be treated as separate severe exacerbations.

The primary statistical objective is to demonstrate that the proportion of subjects who experience severe exacerbations in the subsequent 12-month follow-up (for Year 2, Year 3, Year 4 and Year 5 [in 12-month periods]) is not statistically worse when compared with the proportion of the first 12-months, which begins 6 weeks after the last Alair treatment. This objective will be met if the upper 95% confidence limit of the difference in proportions (i.e., the subsequent 12-month proportion minus the first 12-month proportion) is less than 20%.

2.1.1 Hypotheses

The null and alternative hypotheses for the primary endpoint are as follows:

$$H_o : p_k - p_1 \geq 20\%$$

$$H_a : p_k - p_1 < 20\%$$

where p_1 is the proportion of patients with severe exacerbations at 1 year,
 p_k is the proportion of patients with severe exacerbations at k years and
 $k = 2, 3, 4, \text{ or } 5$.

2.1.2 Sample Size

Under the assumption that in the population of US subjects treated with the Alair System the proportion of patients that experience severe exacerbations will be 0.33 (33% of subjects) or less (based on data from AIR2 Trial - 30.9%, 95% CI 24.2%, 37.7%), a sample size of 200 is adequate to demonstrate durability of the treatment effect at 5 years post-Alair treatment. Up to 300 subjects (minimum of 250 subjects) will be enrolled to achieve at least 200 evaluable study subjects, accounting for a 20% drop-out rate over 5 years. To be counted as an evaluable subject, a subject must have either completed the 5-year visit no earlier than the start of the visit

Study Reference Number E7080

window (1797 days) or have at least 1797 days of study follow-up (see Section 2.1.3) and have primary endpoint data at 5 years.

nQuery Advisor Version 7.0 was used to form a basis for the sample size estimation. The “Two group test of equivalence in proportions (large unequal n’s)” procedure based on a one-sided test at alpha equal to 0.05 and a 20% delta was used to generate the powers presented in Table 1. A minimum of 80% power was achieved for all situations wherein the subsequent year’s assumed proportion of subjects with severe exacerbations was 41% or less. The use of independent samples methodology provides a conservative (over-powered) sample size calculation for matched data on a single sample.

Table 1. Two group test of equivalence in proportions (large unequal n’s) [from nQuery Advisor 7.0]

	1	2	3	4	5	6	7	8	9
Test significance level, α (one-sided)	0.050	0.050	0.050	0.050	0.050	0.050	0.050	0.050	0.050
Standard proportion, π_S	0.330	0.330	0.330	0.330	0.330	0.330	0.330	0.330	0.330
Equivalence limit difference, $\pi_T - \pi_S, \Delta_0$	0.200	0.200	0.200	0.200	0.200	0.200	0.200	0.200	0.200
Test expected proportion, π_T	0.330	0.340	0.350	0.360	0.370	0.380	0.390	0.400	0.410
Expected difference, $\pi_T - \pi_S, \Delta_1$	0.000	0.010	0.020	0.030	0.040	0.050	0.060	0.070	0.080
Power (%)	99	99	99	98	97	95	92	88	83
n_S	250	250	250	250	250	250	250	250	250
n_T	200	200	200	200	200	200	200	200	200
Ratio: n_T / n_S	0.800	0.800	0.800	0.800	0.800	0.800	0.800	0.800	0.800
$N = n_S + n_T$	450	450	450	450	450	450	450	450	450

2.1.3 Statistical Methods

See Section 6.4 for how to identify severe exacerbations.

The proportions of patients with severe exacerbations at each year (p_k , $k=1$ to 5) will be calculated in two ways:

1. Complete Follow-up: using patients who complete the annual follow-up visit or have a follow-up visit (office or phone call) after the visit for that particular year if the annual visit is missed.
2. Complete/Partial Follow-up: using patients who complete the annual follow-up visit no earlier than the start of the follow-up window, have a follow-up visit (office or phone call) after the visit for that particular year if the annual visit is missed, have sufficient follow-up for the year, or had a severe exacerbation during the time period regardless of the amount of follow-up. Sufficient follow-up is having any follow-up visit (office or phone call), adverse event onset date, or hospitalization date that gives the patient at least the number of days of follow-up after the last BT procedure + 42 days given in Table 2.

Table 2. Days for sufficient follow-up by follow-up time

Study Reference Number E7080

Time	Days for sufficient follow-up after the follow-up period starts*
1 Year	337 days
2 Years	702 days
3 Years	1067 days
4 Years	1432 days
5 Years	1797 days

* - the follow-up period starts at last BT procedure + 42 days. The number of days in this column represents the start of the follow-up window after the follow-up period starts and is calculated as # years times 365 days minus 28 days.

All analyses will be done for patients with Complete and Complete/Partial Follow-up. Point estimates and 95% confidence intervals for the proportion of subjects experiencing severe exacerbations during each of the 12-month evaluation periods will be provided. Additionally, the exact upper 95% confidence limit for the difference between the subsequent 12-month proportions and the first 12-month proportion will be calculated, based on methods assuming paired samples; in this analysis, each subsequent 12-month proportion would represent comparisons between the first-year proportion and the second-, third-, fourth-, and fifth-year proportions.

An exact upper 95% confidence limit of the difference between the subsequent 12-month proportions (for Years 2, 3, 4, and 5) compared to the first 12-month proportion for patients with data at both year 1 and year k that is less than 20% will reject the null hypothesis in favor of the alternative hypothesis and demonstrate that the proportions are not substantially worse during each of the subsequent evaluation periods.

Final conclusions regarding the durability of effectiveness (beyond 1 year) will be based on completing the 5 year follow-up of all subjects who are still in the study at that time.

A sensitivity analysis (tipping-point analysis) will be performed to assess the impact of patients with inadequate follow-up on the evaluations of the primary endpoint. The tipping-point analysis will be on the primary endpoint using matched pairs and will be performed as follows: assuming no loss to follow-up and given the observed number of patients evaluated at 1 year and k years, for all combinations of success/failure for patients with missing data, the primary endpoint will be evaluated until the point at which the conclusion of the study changes.

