6.4 Identification of Severe Exacerbations (SE)

1. Filter the medication data (MEDS) to keep all courses of oral corticosteroids (CLASS3=OCS) and other medications that are intravenous uses of the same medications - identify those by looking for CLASS3='Other Specify' and lowercase(CLSSP) with values: 'intravenous corticosteriod' 'intravenous corticosteroid' 'cortcosteroid iv' 'corticosteroid iv'. Note there are spelling mistakes in the entered data.
2. Merge the medication data with the AE data by patient and AE related number (RELAENO) on the medication data with AENUM on the AE data.
3. Use the onset date and the resolution date of the AE to determine the length of the SE. If an AE has no resolution date, impute the date of the most recent follow-up (scheduled or

Study Reference Number E7080

unscheduled) as the resolution date. For partial onset and resolution dates, impute dates as described in Section 6.3.

4. When an AE matches with a course of medication, the AE is considered to be an SE, however, when AEs that are SEs occur too close together, the combined AEs are one SE. If the resolution date of one AE selected as an SE is \leq 6 days before the onset date of another AE that is an SE, then combine the AEs into one SE. There could be more than two AE combined into a single SE.
5. SEs are classified in the time period where the onset date of the SE occurs regardless of the duration of the SE.
6. For each time period, count the number of SEs for each patient and whether the patient has an SE or not. Two types of summaries will be done for the SEs (also ER visits and hospitalization) to include the following patients: (1) patients with the follow-up visit or later visit for that time period, and (2) patients from (1) and patients with any SE in the time period.

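### SAP 2.1.3 and SAP 6.4 define the Complete/Partial follow-up set differently, and the Complete set has no earliest date for the annual visit

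*SAP*

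**What the plan says.** SAP 2.1.3 computes the proportion with a severe exacerbation (SE) in each year on two sets and runs every analysis on both.

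- **Complete (item 1):** "using patients who complete the annual follow-up visit or have a follow-up visit (office or phone call) after the visit", the later contact being the substitute when the annual visit is missed. No earliest date is given for the annual visit.
- **Complete/Partial (item 2):** "using patients who complete the annual follow-up visit no earlier than the start of the follow-up window", or a later contact if the annual visit was missed. Further routes in are to "have sufficient follow-up for the year, or had a severe exacerbation during the time period regardless of the amount of follow-up". On the first of these, "Sufficient follow-up is having any follow-up visit (office or phone call), adverse event onset date, or hospitalization date" reaching the Table 2 day is enough; that day is "calculated as # years times 365 days minus 28 days".

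SAP 2.1.3 opens with a pointer: "See Section 6.4 for how to identify severe exacerbations". SAP 6.4 step 6, which counts SEs and flags whether each patient had one, names two sets of its own. Its first set is given as "1) patients with the follow-up visit or later visit for that time period". Its second set, which adds to the first only through an event, is given as "2) patients from (1) and patients with any SE in the time period".

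SAP 2.1.2 counts a subject as evaluable at 5 years only with a 5-year visit no earlier than day 1797 or at least 1797 days of follow-up, together with 5-year endpoint data.

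**The concern.** There are two defects.

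**Between sections.** The second set in 6.4 lacks both the window condition and the Table 2 route of item 2 in 2.1.3. A programmer following 6.4 and one following 2.1.3 would build different denominators for the same proportion, and no sentence says which section governs.

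**Within 2.1.3.** The set whose name suggests the stricter rule has the looser date rule. A subject whose Year 5 visit took place before day 1797, with nothing afterwards, is not evaluable under 2.1.2 but counts as Complete. The unobserved end of that year is then scored as free of exacerbations.

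Year 5 is where this matters. In Years 1 to 4 the quarterly calls (Protocol 7.3.12) usually supply a later contact. After the 5-year evaluation the subject exits (Protocol 7.3.14) and no later contact is scheduled. Final durability conclusions rest on completion of the 5-year follow-up.

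**Working it through.** **1. The plan's own figures.** Table 2: 365k − 28 for k = 1 to 5 gives 337, 702, 1067, 1432 and 1797 days, as printed. Last column of Table 1: Φ((0.20 − 0.08)/√(0.33×0.67/250 + 0.41×0.59/200) − 1.645) = 83.6%, against 83% stated. The plan's level is therefore one-sided 0.05, and 1.645 is used below.

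**2. Who is classified differently.** Every combination of annual visit (early, in or after the window, missed), later contact, sufficient follow-up and SE was compared across the four definitions. Complete and the first set of 6.4 agree throughout. The second sets differ for two types:

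| Type (no SE in the year) | Complete | 6.4 first | 2.1.3 Complete/Partial | 6.4 second |
|---|---|---|---|---|
| A: annual visit before the window, no contact on or after the Table 2 day | in | in | out | in |
| B: annual visit missed, no later visit, but Table 2 days reached (e.g. by an adverse event or hospitalization date) | out | out | in | out |

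Type A is also why Complete is not a subset of Complete/Partial. Neither type has an SE, so for a single year's proportion only the denominator moves.

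**3. Size in one year.** From SAP 2.1.2: 200 subjects and a 33% rate. Assumed: 10 further subjects whose last contact was the Year 5 visit, on average 60 days before the year ended, with constant hazard.

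- h = −ln(0.67) = 0.4005. Risk over 305 of 365 days = 1 − exp(−0.4005 × 305/365) = 28.4%, so 2.84 of the 10 have an observed SE.
- Complete, and the second set of 6.4: (66 + 2.84)/(200 + 10) = 32.8%.
- Complete/Partial in 2.1.3, where the early subjects enter only through an SE: (66 + 2.84)/(200 + 2.84) = 33.9%.
- Truth: 33.0%.

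The two second sets differ by 1.2 points. With 5 such subjects: 67.42/205 = 32.9% against 67.42/201.42 = 33.5%, a gap of 0.6 points.

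**4. Paired test.** Removing a subject at Year 5 also removes that subject's Year 1 result, so p₁ moves unless the two years are independent. Assume a within-subject correlation of 0.28. At 33% against 45% with 200 pairs this gives a standard error of √[(0.2211 + 0.2475 − 2×0.28×√(0.2211×0.2475))/200] = 4.1 points, close to the roughly 4% in Protocol 4.0.

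- At 33% in both years, P(SE in both) = 0.33² + 0.28 × 0.2211 = 0.1708. The Year 1 rate is 0.1708/0.33 = 51.8% in subjects with a Year 5 SE and (0.33 − 0.1708)/0.67 = 23.8% in those without.
- p₁ in the 2.1.3 second set: (66 + 2.84×0.518)/202.84 = 33.3%.
- p₁ in the 6.4 second set: (66 + 2.84×0.518 + 7.16×0.238)/210 = 32.9%.
- The net gap in the difference falls from 1.2 to about 0.8 points.

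**5. Effect on the upper limit.** Start from 200 pairs with p₁ = 0.33 and independent years, and add m subjects who are event-free at year k and have a 33% Year 1 rate. With n₀₁ pairs going from no SE to SE and n₁₀ the reverse, d = (n₀₁ − n₁₀)/n and the limit is d + 1.645 × √(n₀₁ + n₁₀ − (n₀₁ − n₁₀)²/n)/n. This is a normal approximation to the exact paired limit that the SAP plans.

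| p_k before adding | m = 0 | m = 5 | m = 10 | m = 20 |
|---|---|---|---|---|
| 0.41 | 15.9% | 14.8% | 13.7% | 11.8% |
| 0.45 | 20.0% | 18.8% | 17.6% | 15.5% |

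The limit moves about 1 point for every 5 movable subjects in 200. At 41%, the highest rate in Table 1, no row entry approaches 20%; at 45% the limit starts on the margin.

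**The case against.** **2.1.3 governs the test.** It cites 6.4 only for identifying SEs, which is the numerator, and step 6 speaks of summaries that also cover ER visits and hospitalizations, which carry no hypothesis. That reading is reasonable. But step 6 also determines whether each patient has an SE and names the sets for it, and precedence is not stated. Even on this reading, item 1 still lacks a date floor.

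**The affected group is small.** Protocol 7.3.13 schedules annual visits within 4 weeks either side, so a visit well before the window is a deviation, and in Years 1 to 4 a later call usually restores the subject. This stands, and it confines the issue largely to Year 5. It is not wholly a matter of deviations: the protocol window runs from the 6-week visit (itself ±1 week) and the SAP window from last procedure + 42 days. With 365-day years, a compliant Year 5 visit can fall on day 35 + 1797 = 1832 after the last procedure, 7 days before the SAP's 42 + 1797 = 1839.

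**Both sets are reported and a tipping-point analysis is planned.** This helps in part. The tipping-point analysis varies outcomes for patients with missing data; a subject already counted as Complete need not be among them.

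**A stronger reading.** A reader might infer that every primary denominator depends on the section followed, or that Complete's missing floor materially favours a durability finding. The documents support neither. The first set is identical in both sections, and in the illustration Complete is 0.2 points from the truth, nearer than Complete/Partial in 2.1.3 at 0.9 points. The larger figure of about 1 point is a gap between two definitions, not the bias of either. Nor is the direction uniform: in the separate yearly estimates, the same type of subject at Year 1 lowers p₁ and so raises the difference.

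**Conclusion.** The inconsistency is real and limited. The second follow-up set has two definitions without stated precedence, and Complete has no earliest date, which puts it outside Complete/Partial and at odds with the evaluability rule in 2.1.2. With 10 assumed early last visits, the two second sets differ by about 1 point (1.2 unpaired, about 0.8 paired at a correlation of 0.28). With 5 such visits the unpaired gap is 0.6 points. The number of early last visits, the 60-day average, the constant hazard and the correlation are assumptions, since the documents give none of them. A result near the 20% margin could depend on the choice; one well inside it would not. The edit is worth making because it settles who enters a primary denominator before the data are analysed.

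**What to change.** 1. In SAP 2.1.3 item 1, require either an annual visit no earlier than the Table 2 day, or any later visit or call on or after that day, whether the annual visit was early or missed. Use the same wording for those two routes in item 2. Subjects with an early annual visit but later contact then stay in, and Complete becomes a subset of Complete/Partial. A floor on the annual visit alone would wrongly drop those subjects.
2. In SAP 6.4 step 6, delete the separate patient-set definitions for SE summaries and refer to the two sets in 2.1.3.

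The cost is two wording changes and one programming flag. A few subjects whose last contact was early leave Complete for that year; in the illustration it becomes 66/200 = 33.0%. The edit does not alter entry to Complete/Partial through an SE regardless of follow-up, so that set stays at 33.9% in the illustration.
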